In this study, we seek to investigate the potential effect of IV oxytocin on chronic pain and its functional consequences in individuals with hypermobile Ehlers Danlos syndrome. Chronic pain will be assessed both by pain scales and by patient-reported outcomes. Functional consequence of chronic musculoskeletal pain will be evaluated using ACTIHEART - a chest-worn device using self-adhesive ECG electrodes that records heart rate, inter-beat-interval (IBI), and physical activity.

Section D: Purpose and Objectives

The purpose of this pilot study is to evaluate effect of IV oxytocin on chronic pain in patients with hypermobile Ehlers Danlos syndrome. The study will evaluate chronic pain before and after treatment with IV oxytocin.

Primary outcome measure 1) Change in the individual's subjective reported pain following treatment with placebo

compared to the change in reported pain following treatment with oxytocin as assessed by the following questionnaires: Numerical pain rating scale, Brief Pain Inventory, and McGill Pain Questionnaire.

Secondary Outcome measures 1) Change in heart rate patterns and activity level following treatment with placebo compared to the change in heart rate patterns and activity level following treatment with oxytocin as an objective functional outcome of pain. 2) Change in reported signs of depression and anxiety following treatment with placebo compared to the change in the reported signs following treatment with oxytocin as assessed by Hospital anxiety and depression scale and State-Trait Anxiety Inventory questionnaires.

Section E: Protocol Risks/Subjects

E1. Risk Category

Category 2: Research involving greater than minimal risk, but presenting the prospect of direct benefit to the individual subjects.

E2. Subjects

Gender:

Female

Age:

Adult (18-64 yrs)

Ethnicity:

All Ethnicities

Primary Language:

English

Groups to be recruited will include:

Patients

Which if any of the following vulnerable populations will be recruited as subjects?

Vulnerable populations require special protections. How will you obtain informed consent, protect subject confidentiality, and prevent undue coercion?

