- C. Post Infusion Period 2 Pain & Anxiety Evaluation for 6 days: Participants will complete questionnaires over six days at the investigator's discretion: BPI, NRS, McGill on days 1, 3, and 5 after infusion and HAD and STAI-state and trait questionnaires on day 6 after infusion. Participants will be instructed to mail back the device after completing three days of their last infusion using a prepaid FedEx air bill that will be sent to them by study staff. *Note: The dose oxytocin administration is based on the American College of Obstetricians and Gynecologists' (ACOG) Practice Bulletins for postpartum hemorrhage (see addendum). From the bulletin: Many organizations have recommended active management of the third stage of labor as a method to reduce the incidence of postpartum hemorrhage. Prophylactic oxytocin, by dilute intravenous infusion (bolus dose of 10 units), or intramuscular injection (10 units), remains the most effective medication with the fewest adverse effects". This clinical protocol allows the administration of bolus of oxytocin in a rate of 333 mU/min. We will administer only 1 unit of oxytocin over 40 minutes rate of 25mU/min to avoid any adverse effects.

Texas Children's Hospital REDCap platform may be used for data collection purposes.

Section G: Sample Size/Data Analysis

G1. Sample Size

How many subjects (or specimens, or charts) will be used in this study?

Local: 20 Worldwide: 20

Please indicate why you chose the sample size proposed:

There are no published and validated data regarding the distribution of pain scores in individuals with EDS. From our clinical experience and the fact that the inclusion criteria require patients have chronic pain, it would be reasonable to estimate the mean pain levels without any oxytocin treatment to be 7 on the BPI scale. With a sample size of 17 individuals who will undergo treatment with placebo and oxytocin (i.e., matched pairs), we will be able to detect a mean difference in BPI scores of 2 or greater with oxytocin as compared to the placebo with a two sided test with alpha error of 0.05 and power of 0.8. This analysis is based on an estimated effect size index dz of 0.73, an SD in the oxytocin group of 0.66 x mean, the SD in the placebo group being 1.25 x mean, and the correlation between the measures being 0.15. Additionally, we will enroll 3 more participants to account for a drop out rate of 15%. Thus the total sample size would be 20

G2. Data Analysis

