Provide a description of your plan for data analysis. State the types of comparisons you plan (e.g. comparison of means, comparison of proportions, regressions, analysis of variance). Which is the PRIMARY comparison/analysis? How will the analyses proposed relate to the primary purposes of your study?

The primary goal of this study is to compare the change in pain scores between the pre and post placebo treatment period vs pre and post IV oxytocin treatment period.

Changes from baseline to endpoint will be evaluated by paired T test

Baseline and endpoint that will be compared:

- 1) Maximum pain level, minimum pain level, average pain, and pain-effect scores (using the BPI) in the days prior to each infusion period (placebo and oxytocin) and maximum pain level, minimum pain level, average pain and pain-effect scores (using the BPI) in the days prior to each infusion period (placebo and oxytocin) and average pain and pain-effect scores in the days after each infusion period.
- 2) Comparing the difference in maximum pain level, minimum pain level, average pain and pain-effect scores (using the BPI) pre and post infusion between placebo and oxytocin treatment.
- 3) Simple pain scale scores (NPRS) prior to infusion and simple pain scale scores 2 hours after the infusion on every day of infusion in both infusion periods (placebo and oxytocin).
- 4) Anxiety and depression scores prior and post infusion periods and comparing scores following placebo and oxytocin treatments
- 5) Changes in heart rate, inter-beat-interval (IBI), and physical activity as measured by ACTIHEART comparing data collected prior, during and after placebo and oxytocin treatments.

In addition we will compare heart rate, blood pressure with oxytocin infusion compared to levels with placebo. We will compare oxytocin levels in the plasma prior to the first infusion, immediately after the first infusion and 2 hours after the first infusion for both placebo and oxytocin.

P-values of 0.05 or less will be considered statistically significant

Section H: Potential Risks/Discomforts

H1. Potential Risks/Discomforts

Describe and assess any potential risks/discomforts; (physical, psychological, social, legal, or other) and assess the likelihood and seriousness of such risks:

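### The 0.05 significance rule in G2 covers every secondary comparison, with no adjustment, link to the primary result or exploratory label

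*Combined protocol and SAP*

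**What the plan says.** Section D names one primary outcome, change in reported pain under placebo against change under oxytocin, measured by three questionnaires. It names two secondary outcomes. The first is heart rate patterns and activity level, described "as an objective functional outcome of pain". The second is depression and anxiety, measured by the HAD and STAI.

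Section G2 restates the pain comparison as the primary goal and gives the test: "Changes from baseline to endpoint will be evaluated by paired T test". Items 1 to 3 are pain scores. Item 4 reads "Anxiety and depression scores prior and post infusion periods and comparing scores following placebo and oxytocin treatments". Item 5 reads "Changes in heart rate, inter-beat-interval (IBI), and physical activity as measured by ACTIHEART comparing data collected prior, during and after placebo and oxytocin treatments". A further paragraph adds heart rate, blood pressure and plasma oxytocin comparisons. The section then ends: "P-values of 0.05 or less will be considered statistically significant".

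Section G1 bases the sample size on 17 matched pairs and a "two sided test with alpha error of 0.05 and power of 0.8". Sections D and F1 call the study a pilot.

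**The concern.** The closing sentence of G2 is a stated rule, and nothing limits it to pain. Read as written, any anxiety, depression, heart rate, IBI or activity comparison that reaches 0.05 may be called statistically significant, whatever the pain result. With several such comparisons in a small trial, the chance that at least one reaches 0.05 by luck is well above 5%.

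What is at stake is the wording of the conclusions. Because Section D presents the Actiheart data as an objective reflection of pain, an isolated Actiheart finding is the one most likely to be read as support for an analgesic effect when the pain comparison itself shows none.

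**Working it through.** **The plan's own figure first.** G1 states: "This analysis is based on an estimated effect size index dz of 0.73". For a paired t test with 17 pairs, the noncentrality is 0.73 × √17 = 3.01 and the two-sided 5% critical value on 16 degrees of freedom is 2.120. Power is 80.7% with 17 pairs and 77.9% with 16, so 17 is the smallest number that reaches 80%. Allowing for 15% dropout, 17 / 0.85 = 20. The stated sample size follows from the stated dz. The documents give no error rate across outcomes to reproduce.

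**Counting the secondary contrasts.** Each contrast is one paired test of the change under oxytocin minus the change under placebo. G2 does not give a count, so three readings are shown.

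- Four: HAD, STAI, heart rate, activity.
- Seven: HAD anxiety, HAD depression, STAI-state, STAI-trait, heart rate, IBI, activity. The HAD split is inferred. The general questionnaire list in F2 mentions only the STAI trait part, whereas the descriptions of both treatment periods use state and trait.
- Ten: the four mood scores plus three Actiheart variables in two windows (prior to during, prior to after), 4 + 3 × 2 = 10.

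These counts leave out the within-period pre/post tests and the added heart rate, blood pressure and plasma comparisons.

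**Chance of at least one p ≤ 0.05 when every true difference is zero.** For k independent tests it is 1 − 0.95^k:

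- k = 4: 1 − 0.8145 = 0.185
- k = 7: 1 − 0.6983 = 0.302
- k = 10: 1 − 0.5987 = 0.401

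Correlation lowers these values. The documents give no correlation among the secondary outcomes; the 0.15 in G1 relates the placebo and oxytocin pain measures and does not apply here. A common correlation of 0.5 or 0.8 is therefore an assumption. Paired t tests were simulated with n = 17 and all nulls true, 200,000 trials per cell:

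| Contrasts | Correlation 0 (formula) | 0.5 | 0.8 |
|---|---|---|---|
| 4 | 0.185 | 0.159 | 0.118 |
| 7 | 0.302 | 0.237 | 0.155 |
| 10 | 0.401 | 0.297 | 0.181 |

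Even one contrast per secondary outcome (k = 2) gives 0.098, 0.091 and 0.079.

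These figures count results in either direction. Counting only results that favour oxytocin, independent tests give 1 − 0.975^4 = 0.096 for four and 1 − 0.975^7 = 0.162 for seven, against a nominal 0.025.

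**The case against.** The best defence is that this is a 20-participant pilot. Section D separates primary from secondary outcomes, G2 repeats that pain is the primary goal, and no decision is tied to a secondary result. Formal error control across secondary outcomes is not obligatory in such a study. Much of that stands, and it is why the remedy below is a change of label and not a multiplicity procedure. It does not rescue the closing sentence, because the pilot label is never attached to the tests and the rule gives exploratory results confirmatory wording.

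A reader might infer more than the documents support:

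- *A single risk figure, such as one in five.* For seven contrasts that needs a common correlation of about 0.65, which the documents do not give. Only a range can be defended.
- *Seven as a minimum count.* It rests on an inferred HAD split, and a narrower reading gives four.
- *No hierarchy at all.* Primary and secondary tiers exist. What is missing is any consequence of the tiers for testing.
- *Heart rate and IBI as duplicates, so that one should go.* They correspond beat by beat, but Section D speaks of heart rate patterns, and the variability of IBI is not a transform of mean heart rate. The documents do not say which summary is meant.
- *A plan to let Actiheart override a null pain result.* No section says so. The rule merely leaves that claim open.

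**Conclusion.** The point holds as a gap in the significance rule. Under G2 as written, the chance of at least one false secondary finding is about 12 to 19% for four contrasts, 15.5 to 30% for seven and 18 to 40% for ten. This assumes 17 pairs, a common correlation between 0 and 0.8, and no true difference between the two periods' changes on any secondary outcome. The count and the correlation are assumptions, and the documents set no tolerable error across outcomes to compare with. The direction of the conclusion depends on neither: two contrasts at correlation 0.8 still give about 8%.

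The primary pain comparison and the sample size are not affected by this point. It is a cheap improvement that governs what may be concluded from an isolated secondary result.

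**What to change.** Replace the closing sentence of G2 with two statements.

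1. The two-sided 0.05 rule applies only to the primary pain comparison, the change under oxytocin against the change under placebo, named as one contrast. One of the BPI scores in item 2 would be a natural choice, since the sample size was calculated on the BPI. This naming has to come first: Section D lists three pain questionnaires, and items 1 to 3 of G2 list several pain scores, so at present there is no single primary contrast for the rule to attach to.
2. Items 4 and 5 and the added heart rate, blood pressure and plasma oxytocin comparisons are exploratory. They are reported as estimates with 95% confidence intervals and are not described as statistically significant.

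It would also help to state which HAD and STAI scores and which Actiheart summaries and time windows will be reported.

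The cost is a few sentences, with no new data, visits or participants. Choosing the single pain contrast takes some thought. The downside is that a lone secondary p-value of 0.05 or less can no longer be claimed as an effect of oxytocin.
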